#### **8.1.2. Rechallenge**

Subjects who temporarily discontinued study treatment due to a non-serious AE will be closely monitored during rechallenge. A recurrence of the original AE, or a worsening of the AE, will result in permanent discontinuation of that subject from the study.

### **8.2. Withdrawal from the Study**

The study inclusion and exclusion criteria for enrollment must be followed explicitly. If a subject who does not meet enrollment criteria is inadvertently enrolled, that subject shall be withdrawn from the study.

A subject may withdraw from the study at any time at his/her own request, or may be withdrawn at any time at the discretion of the Investigator for safety, behavioral, compliance, or administrative reasons.

Additionally, this study may be terminated at the discretion of the Sponsor. The Sponsor may stop the study at any time for safety, regulatory, legal, or other reasons aligned with Good Clinical Practice (GCP).

If the subject withdraws consent for disclosure of future information, the sponsor may retain and continue to use any data collected before such a withdrawal of consent.

If a subject withdraws from the study, he/she may request destruction of any samples taken and not tested, and the Investigator must document this in the site study records.

See SoA for data to be collected at the time of study discontinuation and follow-up and for any further evaluations that need to be completed. All the enrolled subjects withdrawn from the study are encouraged to complete all end-of-study (EOS) or early termination (ET) assessments.

When a subject withdraws from the study, the reason(s) for withdrawal shall be recorded by the Investigator in the subject's source documents and on the relevant page of the electronic case report form (eCRF).

### **8.3. Lost to Follow Up**

A subject will be considered lost to follow-up if he or she repeatedly fails to return for scheduled visits and is unable to be contacted by the study site.

The following actions must be taken if a participant fails to return to the clinic for a required study visit:

- The site must attempt to contact the subject and reschedule the missed visit as soon as possible and counsel the participant on the importance of maintaining the assigned visit schedule and ascertain whether or not the participant wishes to and/or should continue in the study.
- Before a subject is deemed lost to follow up, the Investigator or designee must make every effort to regain contact with the participant (where possible, 3 telephone calls and, if necessary, a certified letter to the participant's last known mailing address or local equivalent methods). These contact attempts should be documented in the participant's medical record.
- Should the subject continue to be unreachable, he/she will be considered to have withdrawn from the study with a primary reason of lost to follow-up.

#### **8.4. Replacements**

If a subject is withdrawn from the treatment period of the study for reasons not associated with LT3001 drug product-related safety considerations, the subject will be replaced with another subject assigned to the same treatment with respect to LT3001 drug product and placebo doses (Part A) or a specific cohort (Part B). Subjects who are replacements will be allocated the same randomization number with the first digit of treatment number being replaced by the number 1 (eg, if randomization number R01001 is replaced, then the replacement number will be R01101).

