### **7.7. Blinding**

Part A is double-blind. The unblinded pharmacist at the study site will prepare the study drug. In order to protect the blinding of the subjects and Investigators, the IV bag will be masked properly. Because of the double-blind design of Part A, the Investigator or designee should treat and evaluate all subjects as though they received LT3001 drug product. Only the pharmacist responsible for treatment

assignment and the biostatisticians generating the randomization code or performing the unblinded PK analyses will be unblinded and will have access to treatment assignments; all other parties involved in the study will be fully blinded until Part A is completed.

For the safety review meeting of Part A, a blinded PK analysis will be conducted after all healthy subjects complete study procedures of Part A and blood PK data will be reviewed in a blind manner in the meeting.

Part B is open-label.

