### **7.8. Breaking the Blind**

A subject's treatment assignment will not be broken until the end of Part A unless, in the Investigator's opinion, knowledge of treatment assignment would alter management of SAEs or non-serious AE of Grade 3 or higher severity. In the event that the blind needs to be broken because of a medical emergency, the Investigator may be unblinded to obtain the subject's treatment assignment. Prior to unblinding a subject's treatment assignment, the Investigator should make every effort to contact the medical monitor to discuss the medical emergency and the reason for revealing the actual treatment received by that subject. If a subject's treatment is unblinded, Lumosa must be notified immediately. The Investigator or designee must clearly document any unblinding event and the documentation must include the subject number, the reasons for treatment unblinding, and the date on which the code was broken.

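### In Part A, replacing a subject whose code the Investigator has already broken discloses the replacement's treatment before the first dose, because replacements take the predecessor's treatment

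*Protocol*

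**What the plan says.** Protocol 8.4 covers subjects withdrawn from the treatment period "for reasons not associated with LT3001 drug product-related safety considerations". Its rule for them is that "the subject will be replaced with another subject assigned to the same treatment with respect to LT3001 drug product and placebo doses (Part A"). In Part B the replacement joins the same cohort. There is no new randomization. As to numbering, a replacement is "allocated the same randomization number with the first digit of treatment number being replaced by the number 1"; in the worked example, R01001 becomes R01101.

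Under Protocol 7.8 the code stays closed for the duration of Part A, with one exception: the Investigator judges that "knowledge of treatment assignment would alter management of SAEs or non-serious AE of Grade 3 or higher severity". For emergencies the section adds that "the Investigator may be unblinded to obtain the subject's treatment assignment".

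Protocol 7.5 states that neither the subject nor the Investigator will know the assignment. Protocol 7.7 lists the pharmacist and certain biostatisticians as the only unblinded parties and adds that "all other parties involved in the study will be fully blinded until Part A is completed".

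Protocol 8.1 stops an individual's dosing in Part A for an adverse event of Grade 3 or higher, with no condition on causality. Under 8.1.1 a subject whose non-serious event resolves may re-join.

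**The concern.** The emergency exception in 7.8 concerns the subject who has the event. Under 8.4, that subject's treatment passes to a new subject who has had no event and for whom nothing justifies unblinding. If the Investigator knows the first assignment, the Investigator also knows the second.

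The Part A primary endpoints in Protocol section 4 include the nature and severity of adverse events and the number of subjects with them. Under Appendix 4 the Investigator grades severity and assigns causality. Those judgments also feed the rule in 8.1 that ends Part A after two related serious or Grade 3 or higher events. A replacement of known treatment would be assessed open-label inside a double-blind comparison with a very small placebo group.

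**Working it through.** The plan states no figure on this point, so the check sets the sections side by side and then sizes the consequence.

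**The sequence that leaks**

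1. A Part A subject has a serious or Grade 3 or higher event, and the Investigator obtains the code (7.8).
2. The subject is withdrawn from the treatment period. Stopping doses under 8.1 is not enough in itself, because 8.1.1 allows some subjects to re-join.
3. The reason is not LT3001-related safety. Otherwise 8.4 calls for no replacement.
4. A replacement is enrolled and takes the same treatment (8.4).

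After step 4 the Investigator knows the replacement's treatment. Nothing in 7.5 to 7.8 or 8.4 exempts a code-broken predecessor from the same-treatment rule or re-randomizes the replacement.

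**Both arms can reach step 4.** An LT3001 subject whose event is judged unrelated would be replaced by a subject known to be on LT3001. A subject found to be on placebo cannot have an LT3001-caused event, so a known placebo replacement would follow if relatedness is settled with that knowledge. Section 8.4 does not say whether it is.

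**Role of the number.** R01001 becomes R01101, and the step can be reversed, so the number identifies the predecessor. With one replacement outstanding, the same-treatment rule alone discloses the treatment. With several, the number shows which replacement belongs to which predecessor, provided site staff see it. Applied again to R01101, the rule returns R01101, so a second replacement in the same slot would duplicate an identifier. That is a separate gap and has no bearing on blinding.

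**Change in the Investigator's knowledge.** Group sizes follow from two statements:

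- 16 subjects at 3:1 (5.1): 12 LT3001 and 4 placebo. Probability of LT3001 = 12/16 = 75%.
- 4 sentinels at 1:1, then 12 at 3:1 (7.4): 2 + 9 = 11 LT3001 and 2 + 3 = 5 placebo. Probability of LT3001 = 11/16 = 68.75%.

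For the replacement of a code-broken subject this becomes 100% or 0% before the first dose.

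**Share of the group affected by one known replacement**

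| Denominator | 12:4 split | 11:5 split |
|---|---|---|
| Intended placebo slots | 1/4 = 25% | 1/5 = 20% |
| Dosed placebo subjects in the Safety Analysis Set | 1/(4+1) = 20% | 1/(5+1) = 16.7% |
| Intended LT3001 slots | 1/12 = 8.3% | 1/11 = 9.1% |

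The second row adds one because the Safety Analysis Set (Protocol 10.2, SAP 5) keeps everyone who took at least one dose, so the withdrawn subject stays in it.

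**The case against.** A reader might infer that every code break in Part A unblinds a later subject. The documents do not support that. All four steps are needed, and a code break followed by withdrawal for an LT3001-related event leads to no replacement.

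A reader might also infer that a broken placebo code obliges the site to replace. Section 8.4 does not say that relatedness is reassessed after unblinding, and 7.7 tells the Investigator to treat and evaluate every subject as though on LT3001. On that basis an event in a placebo subject could be handled as a possible LT3001 safety withdrawal, with no replacement. The placebo route is open but not mandated.

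Nor do the documents show that the numbering makes the link visible to the Investigator. In 7.5 the pharmacist takes the assignment from the code list, and in 7.9 the pharmacist records the randomization number at dispensing. Section 7.9 also gives the Investigator or institution responsibility for accountability records, so visibility is possible, but it is not stated.

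On substance, same-treatment replacement protects a small placebo group. A code drawn at 3:1 would give LT3001 about 75% of the time, so placebo completers could fall from 4 to 3 or from 5 to 4. Part A results are also presented by population (SAP 6.4). If 4 placebo subjects were split evenly, which is an assumption, one cell could fall from 2 completers to 1. The cost is real but limited: the withdrawn placebo subject, once dosed, still counts for safety, and SAP 6.3 states that no hypothesis testing is done. Laboratory endpoints also depend less on the Investigator's judgment than adverse event assessment does.

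**Conclusion.** The point holds in a narrow form. When a subject's code has been broken to the Investigator and that subject is then replaced under 8.4, the same-treatment rule discloses the replacement's assignment before dosing. This is contrary to 7.5 and 7.7, and neither document describes a safeguard.

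The sequence is uncommon, and the documents give no basis for a probability. If it occurs, it affects one subject: 20-25% of intended placebo slots, 16.7-20% of dosed placebo subjects in the Safety Analysis Set, or about 8-9% of intended LT3001 slots. These shares assume 16 randomized subjects, a 12:4 or 11:5 split, a single replacement, and a withdrawn subject who had been dosed. The placebo figures also assume that a placebo subject's withdrawal is classed as not LT3001-related once the code is known.

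This is a cheap improvement of low severity.

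**What to change.** Amend Protocol 8.4 for Part A only:

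- Keep same-treatment replacement when the predecessor's code is unbroken.
- When the code was broken to the Investigator, have the unblinded pharmacist assign the replacement from a pre-generated randomized reserve block, with its ratio fixed in advance.
- Give replacements numbers that do not identify the predecessor and that stay unique if a replacement is itself replaced.
- Hold the link to the predecessor in the pharmacist's file until Part A is unblinded.

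The cost is one paragraph and a short addition to the randomization list. The allocation of completers may differ from plan by one subject, and the replacement for a placebo subject may receive LT3001.

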## 9. Study Assessments and Procedures

Study procedures and their timing are summarized in the SoA ([Section 2](#)). Total volume of blood per subject in each cohort summarized in the Table 7.

Protocol waivers or exemptions are not allowed. Immediate safety concerns should be discussed with the sponsor immediately upon occurrence or awareness to determine if the subject should continue or discontinue study treatment. Adherence to the study design requirements, including those specified in the SoA, is essential and required for study conduct.

All screening evaluations must be completed and reviewed to confirm that potential participants meet all eligibility criteria. The Investigator will maintain a screening log to record details of all subjects screened and to confirm eligibility or record reasons for screening failure, as applicable.

Procedures conducted as part of the subject's routine clinical management (eg, blood count) and obtained before signing of the ICF may be utilized for screening or baseline purposes provided the procedures met the protocol-specified criteria and were performed within the time frame defined in the SoA.

**Table 7 Total Volume of Blood Per Subject in Each Cohort**

Type of Sample	Volume per Sample (mL)	Part A	Part B, Cohort 1	Part B, Cohort 2	Part B, Cohort 3	Part B, Cohort 4
Blood sampling period		Day-30 – Day4	Day-30 – Day15	Day-30 – Day16	Day-30 – Day14	Day-30 – Day14
Coagulation parameters						
Hematology						
Clinical chemistry test						
Virology						
Serum pregnancy test						
Platelet function test						
CYP2C19 genotyping						
PK samples of LT3001						
PK samples of Aspirin,						

Clopidogrel Apixaban, or Dabigatran						
---	--	--	--	--	--	--

Note: An indwelling intravenous cannula may be used for blood sample collection. If a mandarin (obturator) is used, blood loss due to discard is not expected. If blood samples are collected via an indwelling cannula, an appropriate amount (i.e., 1 mL) of fluid slightly greater than the dead space volume of the lock will be removed from the cannula and discarded before each blood sample is taken.

## 9.1. Adverse Events

The definitions of an AE or SAE can be found in [Appendix 4](#).

AEs will be reported by the participant (or, when appropriate, by a caregiver, surrogate, or the participant's legally authorized representative).

The Investigator and any designees are responsible for detecting, documenting, and recording events that meet the definition of an AE or SAE and remain responsible for following up AEs that are serious, considered related to the study treatment or study procedures, or that caused the participant to discontinue the study treatment or study. The severity or intensity of each AE is to be assessed by the Investigator according to the National Cancer Institute Common Terminology Criteria for Adverse Events (CTCAE) v5.0

### 9.1.1. Time Period and Frequency for Collecting AE and SAE Information

All AEs and SAEs will be collected from the signing of the ICF until the follow-up visit at the time points specified in the SoA ([Section 2](#)).

Medical occurrences that begin before the start of study treatment but after obtaining informed consent will be recorded on the Medical History/Current Medical Conditions section of the case report form (CRF) not the AE section.

All SAEs will be recorded and reported to the sponsor or designee within 24 hours, as indicated in [Appendix 4](#). The Investigator will submit any updated SAE data to the sponsor within 24 hours of it being available.

Investigators are not obligated to actively seek AE or SAE in former study participants. However, if the Investigator learns of any SAE, including a death, at any time after a participant has been discharged from the study, and he/she considers the event to be reasonably related to the study treatment or study participation, the Investigator must promptly notify the sponsor.

The method of recording, evaluating, and assessing causality of AE and SAE and the procedures for completing and transmitting SAE reports are provided in Appendix 4.

#### **9.1.2. Method of Detecting AEs and SAEs**

Care will be taken not to introduce bias when detecting AEs and/or SAEs. Open-ended and non-leading verbal questioning of the participant is the preferred method to inquire about AE occurrences.

#### **9.1.3. Follow-up of AEs and SAEs**

After the initial AE/SAE report, the Investigator is required to proactively follow each participant at subsequent visits/contacts. All SAEs will be followed until resolution, stabilization, the event is otherwise explained, or the participant is lost to follow-up (as defined in [Section 8.3](#)).

#### **9.1.4. Regulatory Reporting Requirements for SAEs**

Prompt notification by the Investigator to the sponsor of an SAE is essential so that legal obligations and ethical responsibilities towards the safety of subjects and the safety of a study treatment under clinical investigation are met.

The sponsor has a legal responsibility to notify both the local regulatory authority and other regulatory agencies about the safety of a study treatment under clinical investigation. The sponsor will comply with country-specific regulatory requirements relating to safety reporting to the regulatory authority, Institutional Review Boards (IRB)/Independent Ethics Committees (IEC), and Investigators.

Investigator safety reports must be prepared for suspected unexpected serious adverse reactions (SUSAR) according to local regulatory requirements and sponsor policy and forwarded to Investigators as necessary.

An Investigator who receives an Investigator safety report describing a SAE or other specific safety information (eg, summary or listing of SAEs) from the sponsor will review and then file it along with the Investigator's Brochure and will notify the IRB/IEC, if appropriate according to local requirements.

#### **9.1.5. Pregnancy**

Details of all pregnancies in female participants and, if indicated, female partners of male participants will be collected after the start of study treatment and until 30 days after the last dose.

If a pregnancy is reported, the Investigator should inform the sponsor within 24 hours of learning of the pregnancy and should follow the procedures outlined in [Appendix 5](#).

Abnormal pregnancy outcomes (eg, spontaneous abortion, fetal death, stillbirth, congenital anomalies, ectopic pregnancy) are considered SAEs.

## **9.2. Treatment of Overdose**

The dose level of LT3001 drug product will be calculated by the Investigator or a qualified designee based on the study subject's body weight. Since drug accumulation is not anticipated due to the short half-life of LT3001 and subjects will only receive LT3001 drug product administered by an Investigator or a qualified designee and under close monitoring, it is anticipated that the risk of overdose or medication error will be low.

An overdose is any dose of study treatment given to a subject or taken by a subject that exceeds the dose described in the protocol. Any overdose, with or without associated AEs, must be promptly reported to the Medical Monitor. Overdoses without signs or symptoms do not need to be recorded as AEs; in case of any AEs associated with the overdose, these should be reported on relevant AE/SAE sections in the eCRF.

Overdoses and medication errors will be documented as protocol deviations and communicated to the project manager.

No specific therapy for overdose of LT3001 drug product exists. In the event of overdose or medication error, appropriate therapy for the patient's symptoms and clinical status should be provided.

## **9.3. Safety Assessments**

Planned time points for all safety assessments are provided in the SoA ([Section 2](#)).

### **9.3.1. Physical Examinations**

- A complete physical examination will include, at a minimum, assessments of the Cardiovascular, Respiratory, Gastrointestinal and Neurological systems. Height and weight will also be measured and recorded.
- Investigators should pay special attention to clinical signs related to previous serious illnesses.

### **9.3.2. Vital Signs**

- Body temperature, systolic and diastolic blood pressure, heart rate, and respiratory rate will be assessed after the subject has rested in position at least 3 minutes.
- Blood pressure will be assessed in seated and supine position at predose and 60 minutes after dosing/infusion, only supine position at 20 minutes after dosing/infusion.
- Blood pressure and heart rate measurements will be assessed with a completely automated device. Manual techniques will be used only if an automated device is not available.

### **9.3.3.      Electrocardiograms**

- Single 12-lead ECG will be obtained as outlined in the SoA ([Section 2](#)) using an ECG machine that automatically calculates the heart rate and measures RR, PR, QRS, QT, and QTcF intervals.
- ECG will be measured in a supine position after 5 minutes rest.

### **9.3.4.      Pulse Oximetry**

During Part A, pulse oximetry continuous monitoring will be performed from predose up to 1 hour after each infusion is initiated. Oximetry will be recorded at pre-dose and 20 minutes after infusion is initiated (end of infusion).

### **9.3.5.      Coagulation and Platelet Function Test**

During Part A, platelet function test will measure on Day -1, following the first (Dose 1) and last (Dose 9) dose of LT3001 drug product infusion and end of study visit. Coagulation (PT, INR, aPTT, and TT) will be measured during screening, Day -1, and following the Dose 1, 4, and 9 of LT3001 drug product infusion and follow-up visit.

During Part B, coagulation test will be measured in the screening visit. Platelet function test and coagulation tests will be measured on Day -1, following the last dose of aspirin, clopidogrel, apixaban, and dabigatran 15 minutes and 6 hours 15 minutes, and following aspirin, clopidogrel, apixaban and dabigatran coadministration with the first and last LT3001 drug product infusion and follow-up visit.

### **9.3.6.      Clinical Safety Laboratory Assessments**

See [Appendix 2](#) for the list of clinical laboratory tests to be performed and to the SoA ([Section 2](#)) for the timing and frequency.

The Investigator must review the laboratory report, document this review, and record any clinically relevant changes occurring during the study in the AE section of the CRF. The laboratory reports must be filed with the source documents. Clinically significant abnormal laboratory findings are those which are not associated with the underlying disease, unless judged by the Investigator to be more severe than expected for the participant's condition.

All laboratory tests with values considered clinically significantly abnormal during participation in the study should be repeated until the values return to normal or baseline or are no longer considered clinically significant by the Investigator or medical monitor.

- If such values do not return to normal/baseline within a period of time judged reasonable by the Investigator, the etiology should be identified and the sponsor notified.
- All protocol-required laboratory assessments, as defined in [Appendix 2](#), must be conducted in accordance with the laboratory manual and the SoA.

- If laboratory values from non-protocol specified laboratory assessments performed at the institution's local laboratory require a change in participant management or are considered clinically significant by the Investigator (eg, SAE or AE or dose modification), then the results must be recorded in the CRF.

